12.1. Definitions

12.1.1. Adverse Event Definitions and Classifications

Adverse Event

An adverse event is any untoward medical occurrence in a clinical study subject administered a medicinal (investigational or non-investigational) product. An adverse event does not necessarily have a causal relationship with the treatment. An adverse event can therefore be any unfavorable and unintended sign (including an abnormal finding), symptom, or disease temporally associated with the use of a medicinal (investigational or non-investigational) product, whether or not related to that medicinal (investigational or non-investigational) product. (Definition per ICH)

This includes any occurrence that is new in onset or aggravated in severity or frequency from the baseline condition, or abnormal results of diagnostic procedures, including laboratory test abnormalities.

Note: The sponsor collects adverse events starting with the signing of the ICF (refer to Section [12.3.1](#), All Adverse Events, for time of last adverse event recording).

Serious Adverse Event

A serious adverse event based on ICH and EU Guidelines on Pharmacovigilance for Medicinal Products for Human Use is any untoward medical occurrence that at any dose:

- Results in death
- Is life-threatening
(The subject was at risk of death at the time of the event. It does not refer to an event that hypothetically might have caused death if it were more severe.)
- Requires inpatient hospitalization or prolongation of existing hospitalization
- Results in persistent or significant disability/incapacity
- Is a congenital anomaly/birth defect
- Is a suspected transmission of any infectious agent via a medicinal product
- Is Medically Important*

*Medical and scientific judgment should be exercised in deciding whether expedited reporting is also appropriate in other situations, such as important medical events that may not be immediately life threatening or result in death or hospitalization but may jeopardize the subject or may require intervention to prevent one of the other outcomes listed in the definition above. These should usually be considered serious.

For the purposes of this study, efficacy and safety outcomes will not be considered as adverse events or serious adverse events (See Section 12.3.1, All Adverse Events).

Unlisted (Unexpected) Adverse Event/Reference Safety Information

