12.3. Procedures

12.3.1. All Adverse Events

In this study, recording of only a subset of adverse events is necessary. However, any adverse event of particular concern to the investigator may be recorded in the eCRF to alert the sponsor.

The following are excluded from adverse event collection and reporting, regardless of seriousness or severity. Exempted events will be captured on the eCRF as suspected outcome events only and will be waived from unblinding and exempted from expedited reporting and include:

- VTE-related death (death due to PE or death in which PE cannot be ruled out as the cause)
- MI
- ACS
- Stroke
- TIA
- Symptomatic VTE (lower or upper extremity DVT and PE)
- Bleeding events

If the CEC determines that a suspected event does not meet the criteria for an outcome event as defined in the CEC charter, it will still be excluded from adverse event collection and reporting even if serious criteria were met.

Serious Adverse Events

All serious adverse events that are not outcome events as listed above should be reported to the sponsor as described in Section 12.3.2. While one of the efficacy outcome measures is ACM, any non-VTE-related death will be reported to the sponsor as a serious adverse event.

Certain adverse events are considered to be Adverse Events of Special Interest and should be reported as serious adverse events. These include:

- Suspected severe toxic effect on the bone marrow, such as severe thrombocytopenia (platelet count less than 50,000/ μ L), severe neutropenia (white blood cell count less than 500/ μ L), pancytopenia, aplastic anemia
- Suspected severe hypersensitivity reaction (eg, anaphylaxis, angioedema, severe urticaria, bronchospasm, etc.)
- Severe skin reactions such as Stevens-Johnson Syndrome
- Suspected severe liver injury

Non-Serious Adverse Events

The following should be reported:

- Non-serious adverse events leading to permanent study drug discontinuation
- All severe non-serious adverse events (regardless of relation to study drug) including severe laboratory abnormalities will be collected except the study outcomes.

Any other non-serious adverse events do not require reporting. However, any adverse event of particular concern to the investigator may be recorded in the eCRF to alert the sponsor.

Reporting Timelines and Processes

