All adverse events and special reporting situations, whether serious or non-serious, will be reported from the time any signed and dated ICF is obtained until completion of the subject's last study-related procedure (which may include contact for follow-up of safety). Serious adverse events, including those spontaneously reported to the investigator up to the Day 75 (\pm 5d) visit, must be reported using the Serious Adverse Event Form. The sponsor will evaluate any safety information that is spontaneously reported by an investigator beyond the time frame specified in the protocol.

All adverse events, regardless of seriousness, severity, or presumed relationship to study drug, must be recorded using medical terminology in the source document. Whenever possible, diagnoses should be given when signs and symptoms are due to a common etiology (eg, cough, runny nose, sneezing, sore throat, and head congestion should be reported as "upper respiratory infection"). Investigators must record their opinion concerning the relationship of the adverse

event to study therapy. All measures required for adverse event management must be recorded in the source document and reported according to sponsor instructions.

The sponsor assumes responsibility for appropriate reporting of adverse events to the regulatory authorities. The sponsor will also report to the investigator (and the head of the investigational institute where required) all suspected unexpected serious adverse reactions (SUSARs). The investigator (or sponsor where required) must report SUSARs to the appropriate Independent Ethics Committee/Institutional Review Board (IEC/IRB) that approved the protocol unless otherwise required and documented by the IEC/IRB. A SUSAR will be reported to regulatory authorities unblinded. Participating investigators and IEC/IRB will receive a blinded SUSAR summary, unless otherwise specified.

The sponsor assumes responsibility for appropriate reporting of adverse events to the regulatory authorities. The sponsor will also report to the investigator (and the head of the investigational institute where required) all serious adverse events that are unlisted (unexpected) and associated with the use of the study drug. The investigator (or sponsor where required) must report these events to the appropriate Independent Ethics Committee/Institutional Review Board (IEC/IRB) that approved the protocol unless otherwise required and documented by the IEC/IRB.

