12.3.2. Serious Adverse Events

All serious adverse events occurring during the study must be reported to the appropriate sponsor contact person by study-site personnel within 24 hours of their knowledge of the event.

Information regarding serious adverse events will be transmitted to the sponsor using the Serious Adverse Event Form, which must be completed and signed by a physician from the study site, and transmitted to the sponsor within 24 hours. The initial and follow-up reports of a serious adverse event should be made by facsimile (fax, e-mail).

All serious adverse events that have not resolved by the end of the study, or that have not resolved upon discontinuation of the subject's participation in the study, must be followed until any of the following occurs:

- The event resolves
- The event stabilizes
- The event returns to baseline, if a baseline value/status is available
- The event can be attributed to agents other than the study drug or to factors unrelated to study conduct
- It becomes unlikely that any additional information can be obtained (subject or health care practitioner refusal to provide additional information, lost to follow-up after demonstration of due diligence with follow-up efforts)

Any event requiring hospitalization (or prolongation of hospitalization) that occurs during the course of a subject's participation in a clinical study must be reported as a serious adverse event, except hospitalizations for the following:

- Social reasons in the absence of an adverse event
- Surgery or procedure planned before entry into the study (must be documented in the eCRF).

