6.2. Adverse Events

For the purposes of this study (and after discussion with appropriate regulatory agencies) a value-driven approach to safety data collection will be utilized. Certain non-serious adverse events will not be collected, while certain events will be collected as outcome and therefore not reported as serious adverse events. All data on safety and outcomes will be reviewed regularly by an unblinded IDMC. For AEs that are collected, the verbatim terms reported in the eCRF by investigators to identify adverse events will be coded using the Medical Dictionary for Regulatory Activities (MedDRA).

Treatment-emergent adverse events (TEAE) are defined as those adverse events that start between the first study drug and the last study drug + 2 days.

Summary of the following adverse events will be provided by treatment group:

- Post-baseline (on or after the first study drug) adverse events
- Treatment-emergent adverse events
- Adverse events with onset > 2 days from the stop of study drug
- Post-baseline serious adverse events
- Treatment-emergent serious adverse events (TESAE)
- Serious adverse events with onset > 2 days from the stop of study drug
- Adverse events leading to permanent study drug discontinuation
- Adverse events with outcome of death

In addition, incidences of some of the above adverse events by system organ class and dictionary-derived (preferred) term will be provided.

Additional summaries, listings, or subject narratives may be provided, as appropriate.

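### The hospitalization rule in Protocol 12.3.2 does not except the outcome events that 12.3.1 exempts from SAE reporting, and SAP 6.2 has no step for such events if they arrive as SAEs

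*Protocol*

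**What the plan says.** The protocol adopts selective safety collection. Section 12.1.1 states that "efficacy and safety outcomes will not be considered as adverse events or serious adverse events". Section 12.3.1 opens with "In this study, recording of only a subset of adverse events is necessary" and then lists the exemptions: "The following are excluded from adverse event collection and reporting, regardless of seriousness or severity". The list is VTE-related death, MI, ACS, stroke, TIA, symptomatic VTE and bleeding. These are captured as suspected outcome events only, and they stay out of AE reporting even if the Clinical Events Committee (CEC) later rejects them. On SAEs the same section says "All serious adverse events that are not outcome events as listed above should be reported to the sponsor as described in Section 12.3.2".

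Among non-serious events, severe ones and those leading to permanent discontinuation are required. "Any other non-serious adverse events do not require reporting", although an investigator may enter any event of particular concern.

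Two later sentences are broader. Under the timelines heading of 12.3.1: "All adverse events and special reporting situations, whether serious or non-serious, will be reported from the time any signed and dated ICF is obtained", up to the last study-related procedure. In 12.3.2, any event that requires or prolongs hospitalization "must be reported as a serious adverse event, except hospitalizations for the following". Two items follow: social reasons without an adverse event, and surgery or procedures planned before study entry.

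SAP 6.2 repeats that certain events are collected as outcomes and so are not reported as SAEs. It then summarizes by arm the AEs that are collected, including post-baseline and treatment-emergent SAEs.

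**The concern.** For a subject admitted with an outcome event, 12.3.1 says to enter a suspected outcome event only, while 12.3.2 says an SAE is mandatory. A cautious site will tend to follow the broader obligation. If some do, hospitalized VTE, MI, stroke and bleeding enter the SAE data from those sites and not from others.

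These are the events the drug is meant to prevent or may cause, so their rates are expected to differ by arm. An SAE table that includes an unknown share of them no longer describes safety apart from the outcomes, which is its purpose here. Part of any difference between arms would be efficacy or bleeding counted a second time.

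**Working it through.** The point rests on a comparison of text. The plan gives no figure for it to be checked against.

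**Step 1. Trace one case.** A subject taking study drug is admitted with a symptomatic, non-fatal PE.

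| Provision | Result for this event |
|---|---|
| Protocol 12.1.1 | Neither an AE nor an SAE |
| Protocol 12.3.1, exemption list | Suspected outcome event only, whatever its seriousness |
| Protocol 12.3.1, SAE paragraph | Not sent on to 12.3.2 |
| Protocol 12.3.2, hospitalization rule | SAE required; neither exception applies |
| SAP 6.2 | If entered as an SAE with onset from first dose to last dose + 2 days, counted as treatment-emergent; no removal step stated |

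The same trace applies to a hospitalized MI, ACS, stroke, TIA, DVT or bleed. The conflict is in the current text, not in an amendment log.

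**Step 2. Check the sentence on all adverse events in 12.3.1.** It has no qualifier such as a reference back to the required categories. However, it stands under a timelines heading, it runs from consent to the last procedure, and the paragraphs just before it say which events are reportable. It reads most naturally as setting the window. The next paragraph, which puts all AEs in the source document, is a separate duty and does not conflict with a restricted eCRF. This part therefore needs clarification only.

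**Step 3. Check that the misfiled events would differ by arm.** This concerns direction only.

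- VTE: at the planning hazard ratio of 0.60 with 1:1 allocation, 161 primary events split into about 161/1.6 = 100.6 on placebo and 161 × 0.6/1.6 = 60.4 on rivaroxaban.
- Bleeding: Protocol 1.1.5 reports major bleeding from Day 1 to Day 35 in the earlier rivaroxaban trial in medically ill patients as 43 (1.1%) on rivaroxaban against 15 (0.4%) on enoxaparin/placebo. The present trial excludes subjects at higher bleeding risk, so these rates need not carry over.

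The two contributions pull in opposite directions, so they need not cancel and the sign of the net effect is unknown.

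**Step 4. See whether the net effect can be sized.** It would need the share of outcome events that are hospitalized, the share of sites that follow 12.3.2 literally, and the number of affected subjects who have another SAE anyway. The documents give none of these. The 161 events also include VTE-related deaths, so they cannot stand in for hospitalized non-fatal events.

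**The case against.** The strongest reply is that the rule is clear when Section 12 is read as a whole. Protocol 3.2, the opening of Section 12, 12.1.1, 12.3.1 and SAP 6.2 all state the selective scheme, and 12.3.1 sends on to 12.3.2 only SAEs that are not outcome events. On that reading the hospitalization sentence is general wording that applies after the exemption. The SAP already states that outcomes are not SAEs, and detailed programming rules sit in a separate Data Presentation Specifications document that is not available here. The SAE tables are descriptive, and efficacy and ISTH major bleeding use CEC-adjudicated events.

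Most of this stands. The intent is recoverable, and no confirmatory result is touched. What it does not answer is that 12.3.2 is worded as an obligation with its own exception list, which omits the exempt events. Stating that outcomes are not SAEs also does not say what to do with one that has been entered.

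A reader might go further and infer that AE incidence has no defined numerator, because optional entries are mixed with required ones. The documents do not support that. Optional non-serious entries cannot reach the SAE tables, and AEs leading to permanent discontinuation have their own summary. Variation in site habit under double blinding, with randomization stratified by country, adds noise but has no evident mechanism for bias between arms.

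**Conclusion.** The concern holds in a limited form. A literal reading of 12.3.2 would place hospitalized outcome events in the SAE data, and SAP 6.2 states no step for handling them. The descriptive SAE and treatment-emergent SAE tables could then include VTE and bleeding events whose rates differ by arm. The adjudicated efficacy and bleeding analyses are unaffected. The size cannot be determined, and the documents do not show whether sites diverged.

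Two stronger inferences should be resisted. One is a numerical shift in the SAE difference taken from the 161 planned events. It would require an assumed hospitalization share, literal use of 12.3.2 at every site and the inclusion of VTE-related deaths, and it would leave out the opposing bleeding contribution. The other is that misfiled outcomes would be unblinded through SUSAR reporting. An SAE becomes a SUSAR only if it is also unexpected against the Investigator's Brochure and associated with the drug, and 12.3.1 waives unblinding and expedited reporting for these events.

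**What to change.** 1. **Protocol 12.3.2:** add a third exception, *hospitalization for an event listed as exempt in Section 12.3.1, which is entered as a suspected outcome event*.
2. **Protocol 12.3.1, timelines paragraph:** limit the sentence to *all adverse events required to be reported under this section and special reporting situations*. This is a clarification only.
3. **SAP 6.2, before unblinding:** flag exempt outcome events found in the AE/SAE data, present the SAE and treatment-emergent SAE tables without them, and tabulate the flagged events separately by arm. Include those the CEC rejected. Because 12.3.1 keeps rejected events out of AE reporting, deleting them from the SAE tables could leave a serious event in no table at all.

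Optional AEs of concern to the investigator should stay in the by-arm summaries, since moving them to a listing would remove them from comparison. The cost is two protocol sentences, a note to sites and one additional table. If enrolment has ended, the SAP step still works alone, provided it is fixed before unblinding.

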12.3.2. Serious Adverse Events

All serious adverse events occurring during the study must be reported to the appropriate sponsor contact person by study-site personnel within 24 hours of their knowledge of the event.

Information regarding serious adverse events will be transmitted to the sponsor using the Serious Adverse Event Form, which must be completed and signed by a physician from the study site, and transmitted to the sponsor within 24 hours. The initial and follow-up reports of a serious adverse event should be made by facsimile (fax, e-mail).

All serious adverse events that have not resolved by the end of the study, or that have not resolved upon discontinuation of the subject's participation in the study, must be followed until any of the following occurs:

- The event resolves
- The event stabilizes
- The event returns to baseline, if a baseline value/status is available
- The event can be attributed to agents other than the study drug or to factors unrelated to study conduct
- It becomes unlikely that any additional information can be obtained (subject or health care practitioner refusal to provide additional information, lost to follow-up after demonstration of due diligence with follow-up efforts)

Any event requiring hospitalization (or prolongation of hospitalization) that occurs during the course of a subject's participation in a clinical study must be reported as a serious adverse event, except hospitalizations for the following:

- Social reasons in the absence of an adverse event
- Surgery or procedure planned before entry into the study (must be documented in the eCRF).

12.3.3. Pregnancy

All initial reports of pregnancy must be reported to the sponsor by the study-site personnel within 24 hours of their knowledge of the event using the appropriate pregnancy notification form. Abnormal pregnancy outcomes (eg, spontaneous abortion, stillbirth, and congenital anomaly) are considered serious adverse events and must be reported using the Serious Adverse Event Form. Any subject who becomes pregnant during the study must discontinue further study treatment.

Because the effect of the study drug on sperm is unknown, pregnancies in partners of male subjects included in the study will be reported by the study-site personnel within 24 hours of their knowledge of the event using the appropriate pregnancy notification form.

Follow-up information regarding the outcome of the pregnancy and any postnatal sequelae in the infant will be required.

12.4. Contacting Sponsor Regarding Safety

The names (and corresponding telephone numbers) of the individuals who should be contacted regarding safety issues or questions regarding the study are listed on the Contact Information page(s), which will be provided as a separate document.

13. PRODUCT QUALITY COMPLAINT HANDLING

A product quality complaint (PQC) is defined as any suspicion of a product defect related to manufacturing, labeling, or packaging, ie, any dissatisfaction relative to the identity, quality, durability, or reliability of a product, including its labeling or package integrity. A PQC may have an impact on the safety and efficacy of the product. Timely, accurate, and complete reporting and analysis of PQC information from studies are crucial for the protection of subjects, investigators, and the sponsor, and are mandated by regulatory agencies worldwide. The sponsor has established procedures in conformity with regulatory requirements worldwide to ensure appropriate reporting of PQC information; all studies conducted by the sponsor or its affiliates will be conducted in accordance with those procedures.

13.1. Procedures

All initial PQCs must be reported to the sponsor by the study-site personnel within 24 hours after being made aware of the event.

If the defect is combined with a serious adverse event, the study-site personnel must report the PQC to the sponsor according to the serious adverse event reporting timelines (refer to Section 12.3.2, Serious Adverse Events). A sample of the suspected product should be maintained for further investigation if requested by the sponsor.

13.2. Contacting Sponsor Regarding Product Quality

The names (and corresponding telephone numbers) of the individuals who should be contacted regarding product quality issues are listed on the Contact Information page(s), which will be provided as a separate document.

14. STUDY DRUG INFORMATION

14.1. Physical Description of Study Drug(s)

The study drug supplied for this study is rivaroxaban 10 mg, rivaroxaban 7.5 mg and matching placebo. All study drugs will be provided as round white tablets. The crushed 10 mg tablet has been studied for bioequivalence and approved for administration as a crushed tablet; the crushed 7.5 mg tablet has not been tested.

Refer to the Investigator's Brochure for a list of excipients ¹⁹.

14.2. Packaging

The study drug will be supplied in bottles and dispensed in child-resistant packaging.

